#### **9.1.4.1.2. Infusion Set Changes**

The eCOA system will be used by patients to collect all infusion set changes, including date and time of change, designation of routine or premature change, primary reason for premature change (infusion set kinked, came out, or leaking; empty pump reservoir; infusion site pain or redness; pump occlusion alarm; suspected infusion set occlusion; other).

In the case of suspected infusion set occlusion, patients will choose or enter a new correction bolus from the eCOA diary that corresponds to the time of the suspected occlusion. They will then indicate if the correction bolus was given via pump or via syringe. If more than one correction bolus is given, patients should choose the first non-meal related correction bolus. This information is also critical in order to evaluate the primary objective of the study.

Investigators will review pump occlusion alarms, suspected infusion set occlusions, and premature infusion set changes with patients at each visit.

Any interruption of CSII will need to be documented in the eCRF. When patients resume use of pump following the interruption, the infusion set insertion should be entered as “routine” infusion set change in eCOA.

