#### **9.4.7. Pump Occlusion Alarms and Suspected Pump Occlusions**

Patients will document all pump infusion set changes in eCOA and designate if the change was routine or premature. Patients will select whether the early infusion set change was due to an infusion set failure (kinked, came out, leaking), infusion site complication (pain or redness), empty pump reservoir, pump occlusion alarm, other, or if the early infusion set change was due to a suspected infusion set occlusion defined as unexplained hyperglycemia. In the latter case, patients will choose or add a new correction bolus from the eCOA diary that corresponds to the timing of the suspected infusion set occlusion. They will then indicate if the correction bolus was given via pump or via syringe. Investigators will review pump occlusion alarms and suspected pump occlusions with patients at each visit.

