- whether it is an infusion set failure that meets the secondary endpoint definition (i.e. leads to premature infusion set changes, due to a pump occlusion alarm OR due to unexplained hyperglycemia with blood glucose [SMBG] >250 mg/dL [13.9 mmol/L] that does not decrease by >50 mg/dL within 1 hour [+10 minutes] following a correction bolus delivered via the pump)
- the most recent SMBG within 1 hour before the correction bolus
- the 3 most recent CGM values within 20 minutes before the correction bolus
- the most recent SMBG within 1 hour (+10 minutes) following the correction bolus that was collected prior to the infusion set change
- the most recent SMBG within 2 hours (+10 minutes) following the correction bolus that was collected prior to the infusion set change
- the 3 CGM measures within the time interval of [1 hour-10 minutes, 1 hour+10 minutes] following the correction bolus that were collected prior to the infusion set change
- the 3 CGM measures within the time interval of [2 hour-10 minutes, 2 hour+10 minutes] following the correction bolus that were collected prior to the infusion set change
- the highest ketone testing value within ± 2 hours of the correction bolus
- the highest ketone test value within ± 2 hours of the infusion set change

Similarly, a listing of premature infusion set changes due to pump alarms and a listing of all premature infusion set changes will also be provided. The SMBG values, CGM values, and ketone test values relative to the infusion set change time will be provided. Both date and time

of all infusion set changes will be collected in the database by either eCRF or eCOA (Table ITSI.6.4).

Table ITSI.6.4. Source Data for Infusion Set Changes

Study Period	Infusion Set Changes	Data Source
Lead-in period	First infusion set change	eCRF: First Dose Open Label Lead-in Treatment
	Other infusion set changes- outside of the office visit	eCOA
	Last infusion set change	eCRF: Last Dose Open Label Lead-in Treatment ^a
Period I	First infusion set change	eCRF: First Dose Study Treatment Period I
	Other infusion set changes – outside of the office visit	eCOA
	Last infusion set change	eCRF: Last Dose Study Treatment Period I ^a
Period II	First infusion set change	eCRF: First Dose Study Treatment Period II
	Other infusion set changes – outside of the office visit	eCOA
	Last infusion set change	eCRF: Last Dose Study Treatment Period II ^a
Safety Follow-up	NA	NA

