^a In extremely rare cases where patients stopped treatment on pump but continued to use treatment through syringe until they discontinue from the study, the last dose form will capture the timing of the last dose of treatment in CRF, which will not be the last infusion set change.

The last infusion set change in each treatment period (lead-in, Period I or Period II) occurs only when a patient comes to an office visit or early discontinuation of study treatment. This change is not reflective of patients' behavior regarding infusion set changes, and thus it will not be included in the derivation of time until infusion set changes. Patient-reported premature infusion set changes due to the reason "Other" or patient-reported routine infusion set changes that occur within 1 hour of a previous infusion set change (captured in the case report form [CRF]), will be treated as a redundant entry in eCOA and excluded from all analyses. In addition, any patient-reported routine infusion set change that occurred within 24 hours of a previous infusion set change could have been misreported as routine or are redundant entries in eCOA, and thus will be excluded from all analyses.

Time interval until infusion set change for each infusion set can be derived through a minute-to-day conversion by dividing the time difference between the infusion set change and its previous infusion set change by 1440 minutes. The protocol requires that patients change infusion set every 72 ± 4 hours unless a change is required for failure of the infusion set. To handle potential missing input in eCOA for the infusion set change, time interval until infusion set change greater than 7 days (168 hours) will be excluded. For each treatment period, time interval until infusion set change will be derived by averaging all infusion set changes within the period. The analyses will be conducted by an MMRM model (Model 2) as specified in Section 6.1.

Derivation and analysis of interstitial glucose reduction rate are described in Section 6.12.

Actual and change from baseline in total, basal, and bolus insulin doses and bolus/total insulin dose ratios will be compared between LY900014 and insulin lispro using an MMRM model (Model 1) as specified in Section 6.1. The doses and bolus/total insulin dose ratios for each visit will be calculated as the mean of the doses for the last 3 days prior to the visit. A listing of insulin doses will also be provided, including data collected at Visit 801.

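### The SAP's redundant-entry rules look only backward from a diary entry, so some early-timed copies of a visit set change stay in two secondary endpoints; repeat alarm or occlusion entries have no rule at all (minor)

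*SAP*

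**What the plan says.** The protocol gives the patient diary a wide remit. Protocol 9.1.4.1.2 says "The eCOA system will be used by patients to collect all infusion set changes", and Protocol 9.4.7 says "Patients will document all pump infusion set changes in eCOA and designate if the change was routine or premature".

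The SAP narrows this for analysis. Table ITSI.6.4 takes the first and last change of each period from the eCRF and uses the diary for "Other infusion set changes- outside of the office visit". The SAP regards the last change of a period as driven by the visit and not by the patient, and "thus it will not be included in the derivation of time until infusion set changes".

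SAP 6.11.2 then has two clean-up rules:

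- Routine entries, and premature entries with reason 'Other', are covered if they are ones "that occur within 1 hour of a previous infusion set change (captured in the case report form [CRF"). Each such entry "will be treated as a redundant entry in eCOA and excluded from all analyses".
- On the second rule the SAP reasons that "any patient-reported routine infusion set change that occurred within 24 hours of a previous infusion set change could have been misreported as routine" or could be redundant, and it excludes these entries too. This rule is not tied to a CRF change.

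Neither rule names 'pump occlusion alarm' or 'suspected infusion set occlusion'. The primary rate in SAP 6.11.1 is events divided by exposure days, times 30, with no merging step. For hypoglycemia, by contrast, SAP 6.11.7.1 counts events 30 minutes or less apart as one.

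**The concern.** Patients are told to enter every change, while visit changes come from the eCRF, so some diary copies of visit changes can be expected. The 1-hour rule exists to remove them. It catches a copy timed after the CRF time but not one timed shortly before it. A surviving early copy puts the visit-driven interval back into the time-to-change endpoint, which the same paragraph sets out to prevent. If labelled 'Other', it also counts as a premature change for a reason unrelated to either insulin.

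The second gap concerns the primary rate. If a patient entered one alarm-driven change twice, both entries would count. The trial is meant to assess safety comparability and is not powered for non-inferiority or superiority, so the absolute event rates are a main output.

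**Working it through.** The plan gives no figure for redundant entries. Its one sample-size calculation reproduces (42/0.88 = 47.7, rounded up to 48) and is not involved here.

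**1. The two rules applied literally to test entries**

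| Diary entry | Result |
|---|---|
| Copy 0.3 h after the CRF visit change, routine or 'Other' | removed |
| Copy 0.3 h before it, routine, prior change about 48 h earlier | kept |
| Copy 0.3 h before it, routine, prior change about 20 h earlier | removed by the 24-hour rule |
| Copy 0.3 h before it, 'Other', prior change about 20 h earlier | kept |
| Two routine entries minutes apart at home | one removed |
| Two alarm entries minutes apart | both kept |
| Two suspected-occlusion entries minutes apart | both kept |

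To be analysed at all, an early copy must also be timed at or before the last dose of the period (the on-IP rule in SAP 6.1).

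**2. Share of early routine copies that survive.** Inputs are the 72-hour change interval (SAP 6.11.2) and an assumption that the visit falls uniformly within that cycle. The share more than 24 h after the prior change is (72 − 24)/72 = 67%. Their mean interval is (24 + 72)/2 = 48 h.

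**3. Effect on secondary endpoint 4.** Assume 13 home intervals of 72 h in the 6-week period.

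- With one kept 48 h interval: (13 × 72 + 48)/14 = 984/14 = 70.3 h, a shift of −1.7 h (2.4% of 72 h).
- At the 24 h boundary: (936 + 24)/14 = 68.6 h, a shift of −3.4 h.
- The 24-hour rule does not apply to 'Other' copies, so their interval can be shorter. At 1 h: (936 + 1)/14 = 66.9 h, a shift of −5.1 h.

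**4. Effect on secondary endpoint 3.** One false 'Other' change in 42 days adds 1 × 30/42 = 0.71 events/30 days. It also makes the patient a case for incidence if there was no other premature change.

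**5. Effect of a repeat entry on the primary rate.** One event gives 1 × 30/42 = 0.71, and two entries of it give 2 × 30/42 = 1.43 events/30 days. A repeated alarm entry needs nothing further to count. A repeated occlusion entry counts only if it also meets the bolus and SMBG conditions in SAP 6.11.1.

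**6. Effect on the primary test.** This was simulated with 42 patients, negative binomial counts (dispersion 0.29), a signed-rank test, 3,000 trials per setting, and each event duplicated with probability 0, 5% or 20%. The duplication shares and the rates of 0.1 to 0.44 events/patient/30 days are assumptions. The 0.44 and 0.29 appear only in the deleted power text in the protocol's amendment summary, for a different endpoint definition.

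- Equal rates: type I error was 0.045 to 0.054 throughout. A mean rate of 0.44 rose to about 0.46 at 5% duplication and 0.53 at 20%.
- Rates 0.44 against 0.88: power was 0.81 without duplication and 0.76 at 20%.

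**The case against.** The intent is already in the plan: Table ITSI.6.4 confines the diary to changes outside the office visit, and the last change is dropped from the interval derivation. The site change is made under staff observation after all other visit procedures, and device clocks are to be synchronized at office visits. An entry made after the change will usually be timed at or after the CRF time, where the 1-hour rule works. This stands as a reason to expect few early copies. It does not close the gap, because the table states a source and gives no rule that identifies and removes a copy, and synchronized devices do not make a patient-entered time equal a site-recorded dose time.

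For repeat entries, the objection is stronger. The SAP speaks of redundancy only for routine and 'Other' entries. A reader might infer that alarm and occlusion entries are also duplicated, but the documents do not say so. An occlusion entry requires a linked bolus and a statement of pump or syringe, which makes an accidental repeat less likely. Investigators review these events at each visit, and listings of them are planned. The diary flow chart (Figure ITSI.5.2) is not visible in the text reviewed, so a built-in check cannot be excluded. A new set can also truly fail soon after insertion, so automatic merging in a primary safety count could delete real events. That last argument decides the form of the fix.

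**Conclusion.** The gap is real in the SAP text but narrow, and its severity is minor. An early-timed copy survives only if it is labelled 'Other', or is routine and more than 24 h after the prior change. The cost is about −1.7 h in mean wear for a typical kept routine copy and, for an 'Other' copy, 0.71 false premature changes per 30 days as well, in affected patient-periods only. The wear figure rests on uniform visit timing and 13 regular intervals. How often such copies occur is not known.

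Three stronger readings are not supported:

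- **Every early copy counts as a real change.** The 24-hour rule removes an early routine copy made within 24 h of the prior change.
- **Copies of visit changes inflate the primary endpoint.** They are routine or 'Other' entries, and neither is a primary event. Only a repeat alarm or qualifying occlusion entry would reach the primary rate.
- **The treatment comparison is biased.** Reporting is double-blind, so nothing suggests that duplication would differ by insulin. In the simulation, absolute rates rose by about the duplication share, power fell slightly, and type I error stayed near 0.05.

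**What to change.** In SAP 6.11.2, before unblinding:

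1. Make the CRF window two-sided: treat any routine or 'Other' diary entry within 1 hour before or after a CRF-captured change as that same change. The cost is one line of wording and minor programming. A genuine routine or 'Other' change in the hour before a visit would be dropped.
2. Keep all alarm and suspected-occlusion entries in the main primary analysis. Flag same-reason entries within 1 hour of each other in the listings already planned, and add one sensitivity analysis that repeats the primary signed-rank test with each such set counted as one event. The cost is a flag and one extra table. Genuine early re-failures stay in the main count.

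Sample size is unaffected.

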Pump interruption is defined as patient is off pump due to pump malfunction and is temporarily using injection therapy. It does not include the condition where patient uses a syringe to inject a correction bolus dose while still on pump. Any interruption of CSII will need to be documented in the electronic case report form (eCRF). When patients resume use of pump following the interruption, the infusion set insertion should be entered as “routine” infusion set change in eCOA.

[figure not shown]

Figure ITSI.5.2. Flow chart for reporting infusion set changes.

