Eligibility	Inclusion/Exclusion	Other Inadvertent Enrollment	Non Programmable (monitoring)	Identified by CRA as captured in sCTMS.
Eligibility	Inclusion/Exclusion	Use of non-study device or materials	Non Programmable (monitoring)	Use of non-study pumps, infusion sets, and use of Enlite sensor (enables Smart-Guard)
Investigational Product	Treatment Assignment/ Randomization Error	N/A	Non Programmable (monitoring)	IWRS data entry errors that impact patient stratification, for example, lab data indicated different strata from IWRS stratification report. Dispensing error: Patient is assigned to a treatment, but site gave a different treatment to the patient.
Investigational Product	Unblinding	N/A	Non Programmable (monitoring)	Any inadvertent unblinding affecting, patients, investigator or sponsor.
Investigational Product	Patient Took Medication Not Fit for Use	N/A	Non Programmable (monitoring)	Study Drug not fit for use administered to patient.

Category	Sub-categories	Trial Specific	Source	Methods of Identification
Investigational Product	Other	Use of expired CT material	Non Programmable (monitoring)	Also identified by CRA as captured in sCTMS.
Study Procedures	Other	Infusion set change frequency	Programmable (clinical database)	eCOA data indicate that $\geq 75\%$ of routine infusion set changes are not in the range of 72 ± 4 hours during the two 6-week treatment periods (#13).
Study Procedures	Violation of Discontinuation Criteria	N/A	Mixed (monitoring and clinical database)	Patients not discontinued from study despite having met protocol specified discontinuation criteria. Also identified by CRA as captured in sCTMS. Protocol Section 8 (e.g., patient(s) become pregnant according to central/local lab or CRF AE page).
Study Procedures	Excluded Conmeds	N/A	Mixed (monitoring and clinical database)	CRF Prior Diabetes Therapies / Concomitant Therapy panel data to indicate not compliant with entry criteria #43 and study-specific restriction on concomitant therapies Table ITSI.5 in the study protocol. Also identified by CRA as captured in sCTMS.
Study Procedures	Visit Schedule Criteria	N/A	Programmable (clinical database)	CRF data indicate that two consecutive office visits are completely missing.

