6.11. Safety Analyses

6.11.1. Primary Outcome and Methodology

The primary objective of this study is to compare LY900014 and insulin lispro with respect to the rate (events/patient/30 days) of infusion set failures that lead to premature infusion set changes, due to a pump occlusion alarm OR due to unexplained hyperglycemia with blood glucose (SMBG) >250 mg/dL (13.9 mmol/L) that does not decrease within 1 hour following a correction bolus delivered via the pump, during the 6-week treatment period.

To be considered as the primary endpoint, an infusion set failure must result in a premature infusion set change due to:

1. pump occlusion alarm(s), OR
2. unexplained hyperglycemia that meets the following conditions:
 - Associated with a non-meal-related correction bolus delivered via the pump at least 1 hour before the infusion set change
 - Most recent self-monitored blood glucose (SMBG) within 1 hour before the correction bolus >250 mg/dL (13.9 mmol/L)
 - At least 1 SMBG obtained following the correction bolus prior to the infusion set change
 - Within 1 hour (+10 minutes) following the correction bolus, the most recent SMBG prior to the infusion set change does not indicate a decrease in blood glucose

If more than 1 non-meal-related correction bolus is given for an unexplained hyperglycemia, only the first correction bolus time will be used to determine the 1 hour (+10 minutes) timeframe following the correction bolus as described in Section 9.1.4.1.2 of the protocol.

For each treatment period (lead-in, Period I and Period II), the infusion set failure rate (events/patient/30 days) will be calculated for each patient as the total number of events while the patient is on pump and on study treatment divided by the days of exposure [last dose date and time – first dose date and time – duration of pump or treatment interruption] times 30.

The analyses of the primary objective will be conducted on the Safety Population including data collected prior to permanent discontinuation of investigational product (i.e., last dose) in each randomized treatment period (Period I and Period II) and excluding data (if any) that are collected while patients temporarily are off pump or off IP. Treatment group comparisons will be performed using Wilcoxon signed-rank test at the full significance level of 0.05, with patients who are dosed in both treatment periods.

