6.11.2. Other Secondary Safety Analyses

The analyses described in Section 6.11.2 will include data collected for the Safety Population including data collected prior to permanent discontinuation (i.e., last dose) of IP in each 6-week treatment period. In addition, other than severe hypoglycemia events, all secondary safety endpoints are pump-related, and therefore the corresponding analyses will also exclude data (if any) that are collected while patients temporarily are off pump or off IP.

For the following secondary safety endpoints, the incidence (percent of patients with at least 1 event) and rate will be analyzed using Prescott's exact test and Wilcoxon signed-rank test, respectively, as described above for the primary endpoint.

- suspected infusion set occlusions defined as unexplained hyperglycemia with blood glucose (SMBG) >250 mg/dL (13.9 mmol/L) that does not decrease within 1 hour (+10 minutes) following a correction bolus delivered via the pump and that leads to an infusion set change
- infusion set failures leading to premature infusion set changes due to unexplained hyperglycemia with blood glucose >250 mg/dL that does not decrease by >50 mg/dL within 1 hour (+10 minutes) following a correction bolus delivered via the pump
- premature infusion set changes for any reason and for each individual reason (infusion set kinked, came out or leaking; empty pump reservoir; infusion site pain or redness; pump occlusion alarm; suspected infusion set occlusion; other)
- severe hypoglycemic events

For the infusion set failures and premature infusion set changes, the number of events and the number of patients with events will be derived for each treatment group by infusion set catheter dwell time (≤ 24 hours, >24 and ≤ 48 hours, >48 and ≤ 72 hour, >72 hours), and overall (across over the course of approximately 72-hours of continuous infusion).

A listing of premature infusion set changes due to unexplained hyperglycemia will be generated. For each premature infusion set change due to unexplained hyperglycemia, the following information will be provided:

- whether it is an infusion set failure that meets the primary endpoint definition

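### The 24-hour exclusion in SAP 6.11.2 can delete real infusion set changes and lengthen the wear interval, and no planned output shows how many entries are dropped

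*SAP*

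**What the plan says.** SAP 6.11.2 has two cleaning rules for patient-reported set changes. The first treats certain entries within 1 hour of a change captured in the CRF as redundant. The second goes further, on the ground that "any patient-reported routine infusion set change that occurred within 24 hours of a previous infusion set change could have been misreported as routine". The same sentence then gives its alternative ground and the consequence: "or are redundant entries in eCOA, and thus will be excluded from all analyses". It makes no exception.

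The wear interval, which is secondary endpoint 4, is obtained by "dividing the time difference between the infusion set change and its previous infusion set change by 1440 minutes". Intervals above 168 h are dropped, the change made at the closing visit of each period is not used, and the rest are averaged per patient and period for MMRM Model 2. Set failures and premature changes are also "derived for each treatment group by infusion set catheter dwell time", in bins cut at 24, 48 and 72 h.

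On pump interruptions, SAP 5.1 says: "When patients resume use of pump following the interruption, the infusion set insertion should be entered as" a routine change. Protocol 9.1.4.1.2 gives the same instruction and adds: "Any interruption of CSII will need to be documented in the eCRF". SAP 6.11.1 already subtracts the "duration of pump or treatment interruption" when it computes exposure for the primary rate.

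The set-change listings in SAP 6.11.2 cover premature changes. The one other check on routine timing is in SAP 6.9, which flags a patient when at least 75% "of routine infusion set changes are not in the range of" 72 ± 4 hours.

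**The concern.** The SAP offers two explanations for an early routine entry: a duplicate, or a change with the wrong label. Exclusion suits the first but not the second. The interval endpoint uses change times only, so a mislabelled change still ended one wear period and began another. A third case is not mentioned: a patient who resumes the pump within 24 h of the last set change, and follows the instruction to record a routine change, has a correctly labelled real insertion removed.

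Because the entry leaves every analysis, the literal reading is that the next interval runs from the last retained change. That is right for a duplicate. For a real change it merges two wear periods, overstates the patient's mean interval, and adds the lost wear to the dwell time of the next failure. The CGM summaries by catheter dwell day in SAP 6.12 shift in the same way.

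At stake are the wear-interval comparison and the dwell-time tables. A bias between products needs such entries to be unequal between products, and nothing planned would show whether they are.

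**Working it through.** The plan states no figure to reproduce. The following are illustrations of what the rule does.

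**Inputs from the documents.** Period of 6 weeks, 42 × 24 = 1008 h (SAP 5.1). Scheduled wear 72 h (Protocol 6.1, criterion 13). Visit change not counted and 168-h upper cut (SAP 6.11.2). About 42 completers (SAP 5.2). **Assumed:** one early routine entry in a period, its time, and the number of patients affected.

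**1. No early entry.** 1008/72 = 14 changes. The last is the visit change, so 13 intervals count and the mean is 72.0 h.

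**2. One real change at 12 h, 72-h wear afterwards.**
- True mean: (12 + 13 × 72)/14 = 948/14 = 67.7 h.
- Next interval from the last retained change: (84 + 12 × 72)/13 = 948/13 = 72.9 h, error +5.2 h.
- For comparison, if only the short interval were lost: 13 × 72/13 = 72.0 h, error +4.3 h.

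| Time of real change | True mean | From last retained change | Short interval only lost |
|---|---|---|---|
| 4 h | 67.1 h | 72.3 h (+5.2) | 72.0 h (+4.9) |
| 12 h | 67.7 h | 72.9 h (+5.2) | 72.0 h (+4.3) |
| 20 h | 68.3 h | 73.5 h (+5.3) | 72.0 h (+3.7) |

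The merged interval is below 72 + 24 = 96 h, so the 168-h cut does not remove it.

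**3. Treatment difference.** With k of 42 patients having one such change on one product only, the difference in mean interval is wrong by 5.21 × k/42. For k = 2, 4 and 10 this is 0.25, 0.50 and 1.24 h. With 4.29 in place of 5.21 it is 0.20, 0.41 and 1.02 h. With equal numbers on both products it is 0.

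**4. Dwell time.** A failure 20 h after an excluded 12-h change belongs in the bin up to 24 h. Measured from the last retained change it is 12 + 20 = 32 h, one bin higher.

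**5. Pump interruption.** Off pump from 6 to 18 h, new set at 18 h, then 13 intervals of 72 h.
- Re-insertion excluded: (90 + 12 × 72)/13 = 73.4 h, or (78 + 12 × 72)/13 = 72.5 h if the 12 off-pump hours are subtracted.
- Re-insertion kept, interrupted wear not counted: 13 × 72/13 = 72.0 h.
- Re-insertion kept, interrupted wear counted: (6 + 13 × 72)/14 = 67.3 h, or (18 + 13 × 72)/14 = 68.1 h without subtracting off-pump time.

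An exemption therefore has to say what happens to the wear that was cut short.

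**6. Opposite error.** If a false entry at 20 h is kept, the mean is (20 + 52 + 12 × 72)/14 = 66.9 h instead of 72.0 h, an error of −5.1 h.

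**7. Visibility.** Thirteen patient-reported changes per period make 26 over both. The deviation flag needs 0.75 × 26 = 19.5, so 20, off schedule. A few excluded entries would not trigger it.

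**The case against.** The rule has a sound basis. Routine changes are due at 72 ± 4 h, and exclusion criterion 31 keeps out patients who regularly change sets more often than every 3 days, so a routine entry within 24 h is suspect on its face. Sites review set changes from eCOA at Visits 2 to 9, and Protocol 9.1.4.1 recommends weekly portal review. The rule treats both products alike in a crossover, and this SAP version was approved before unblinding. The dwell-time outputs are tabulations with no stated test. Even the extreme case above, 10 of 42 patients all on one product, gives about 1.0 to 1.2 h against a permitted window of ± 4 h. A repeat analysis cannot settle the matter, because keeping a duplicate costs about as much as dropping a real change.

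Most of this stands. It justifies keeping the rule as the main analysis and grading the point minor. It does not justify removing insertions that the documents themselves require to be labelled routine, and site review is not described as settling which excluded entries were real.

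A reader might also infer that the start of the next interval is left wholly open. It is not: removal from every analysis points to the last retained change, although one explicit sentence is missing.

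**Conclusion.** The concern holds as a minor point on a secondary endpoint and on descriptive dwell-time tables. A real early change that is excluded overstates that patient's period mean by about 5 h, assuming 72-h wear otherwise and the literal start point. The effect on the treatment comparison is about 0.2 to 1.2 h if 2 to 10 of 42 patients are affected on one product only, and none if the products are equally affected. The documents give no frequency and report no actual case; the interruption case is probably rare, since the re-insertion must fall within 24 h of the previous change.

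Two stronger inferences are not supported. The first is that the rule hides set failures from the primary analysis. A primary event requires a premature change, so an entry labelled routine would not count with or without this rule; the primary rate and the premature-change counts are the same either way. The second is that the rule favours one product. Nothing in the documents indicates that such entries are more frequent on either.

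**What to change.** Before unblinding, amend SAP 6.11.2:

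1. Exempt insertions that follow a pump interruption documented in the eCRF. Start a new interval and a new dwell time there, and state that the wear cut short by the interruption is not counted as a completed interval.
2. Otherwise keep the current rule as the main analysis, and state that the next interval and dwell time run from the last retained change.
3. Count the excluded entries by treatment and period. Repeat the interval and dwell-time analyses, as supportive only, retaining entries more than 1 h after the previous change. Do not relabel unresolved routine entries as premature.

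The cost is a few sentences, one table of counts and one repeat of the interval and dwell-time outputs. No new data are needed, since interruptions are already recorded and already used for exposure in the primary rate. The drawback is that the repeat may keep some duplicates, which pull the interval down. The two analyses therefore bracket the result and do not show which is right.
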